**22. Do you need to move to other centres to perform one of the following?**

- A. Periodical visit [ ]
- B. Specialist visit [ ]
- C. Special examination [ ]

D. Laboratory analysis [ ]  
E. Other (please specify) \_\_\_\_\_

**23. If yes, how far are the centres from your home?**

A. 5-10km [ ]  
B. 10-30km [ ]  
C. 30-50km [ ]  
D. 50-60km [ ]  
E. 60-70km [ ]

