**21. Who pays for your treatment? (tick all that apply)**

- A. My self/my family [ ]
- B. Health insurance (private) mine [ ]
- C. Health insurance (private) my employer's [ ]
- D. State goverment provide free healthcare [ ]
- E. Other (please specify) \_\_\_\_\_

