**24. Are there facilities for psychological support in this hospital?**

A. Yes [ ]  
B. No [ ]

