### SECTION B

**1. Which of the following additional training did you receive on Sickle Cell Disease management in the past three months?**

- A. Seminar [ ]
- B. Conference [ ]
- C. Workshop [ ]
- D. Training [ ]
- E. None of the above [ ]
- F. Other (please specify) \_\_\_\_\_

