**2. How often do you see or attended to Sickle Cell Disease patients?**

- A. Once in a week [ ]
- B. Twice in a week [ ]
- C. Once in a month [ ]
- D. Twice in a month [ ]
- E. Other (please specify) \_\_\_\_\_

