**3. How many Sickle Cell Disease patients do you see or attend in the clinic?**

- A. 5-10 [ ]

B. 10-15 [ ]  
C. 15-20 [ ]  
D. Other (please specify) \_\_\_\_\_

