**4. How many SCD patients do you think is adequate for you to see or attend?**

A. 5-10 [ ]  
B. 10-15 [ ]  
C. 15-20 [ ]  
D. Other (please specify) \_\_\_\_\_

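### Annex I item 22 has no 'No' box, item 23 covers only 5 to 70 km, and Annex II items 3 and 4 name no period

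*Protocol*

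**What the plan says.** Three parts of the printed questionnaires are involved.

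- **Annex I, Section B, item 22** asks "Do you need to move to other centres to perform one of the following". The answers are four kinds of visit or test and an 'Other' line. No box says that no travel is needed.
- **Annex I, Section B, item 23** continues "If yes, how far are the centres from your home". Its bands are 5-10, 10-30, 30-50, 50-60 and 60-70 km, with no 'Other' line.
- **Annex II, Section B, items 3 and 4** ask "How many Sickle Cell Disease patients do you see or attend in the clinic" and "How many SCD patients do you think is adequate for you to see or attend". Both offer 5-10, 10-15, 15-20 and 'Other'. Neither says per day, session, week or month.

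The same forms handle such items properly elsewhere. Annex I item 24, "Are there facilities for psychological support in this hospital", has 'Yes' and 'No' boxes. Annex II item 1 prints "None of the above". Annex I item 21 tells the respondent that several answers are allowed: "Who pays for your treatment? (tick all that apply".

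Section 5.1 makes the forms self-completed after instructions from the investigator. Section 3.2 sets the numbers and announces a wider survey after the pilot.

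**The concern.** Item 23 depends on a 'yes' that item 22 does not collect. A tick in item 22 or an answer in item 23 shows travel. A form blank on both does not show its absence, because the respondent may have skipped the pair, so the share of patients who need another centre has no clear denominator.

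Item 23 has no place for a respondent travelling 3 km or 90 km. Such a person leaves it blank or is pushed into an end band. It also does not say which centre to use when several are visited. As a lesser point, 10, 30, 50 and 60 km each fall in two bands.

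For the caseload items, two workers with the same workload can tick different boxes because one thinks of a day and the other of a week. Annex II item 2 asks how often patients are seen and could convert item 3 to a monthly load, but only if item 3 is per attendance. Its mention of the clinic may hint at that reading. Nothing states it, and item 4 lacks even the hint.

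Section 3.1 puts management of the disease in the clinical centre at the heart of the objective, and both travel for care and staff workload bear on it. An analysis plan can say how blanks are coded, but it cannot add an answer box to a form already filled in.

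**Working it through.** **The plan's own figure.** Sections 3.2 and 3.3 give 30 patients or parents per centre and four centres: 30 × 4 = 120, as stated. The protocol gives no travel, distance or caseload shares, so every share below is assumed for illustration.

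**Item 22.** Let t be the number ticking at least one service and f the fraction of the remaining 120 − t blank forms that are skips. With true skips removed, the share is t / (120 − f(120 − t)).

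| t | f = 0 | f = 0.1 | f = 0.2 |
|---|---|---|---|
| 30 | 30/120 = 25.0% | 30/111 = 27.0% | 30/102 = 29.4% |
| 60 | 60/120 = 50.0% | 60/114 = 52.6% | 60/108 = 55.6% |
| 90 | 90/120 = 75.0% | 90/117 = 76.9% | 90/114 = 78.9% |

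Reading every blank as 'no' therefore understates the share by about 2 to 6 points if 10 to 20% of blanks are skips, and by nothing if nobody skips.

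**Item 23, among travellers.** Suppose 10% truly travel 60-70 km and a fraction p travel farther. The 60-70 km band then reads 0.10/(1 − p) if the farther group leave the item blank, and 0.10 + p if they tick the last band.

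| p | Left blank | Forced into last band | No valid box, of 60 travellers |
|---|---|---|---|
| 0 | 10.0% | 10% | 0 |
| 0.05 | 10.5% | 15% | 3 |
| 0.10 | 11.1% | 20% | 6 |
| 0.20 | 12.5% | 30% | 12 |

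**Annex II item 3.** Take one worker who sees 8 patients per clinic day and ticks "Twice in a week" in item 2. The true load is 8 × 2 = 16 per week, or 16 × 52/12 = 69.3 per month. The honest answer to item 3 is 5-10 if the worker thinks per day, 15-20 if per week, and 'Other' if per month.

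- 15-20 meant per week but read per attendance: 15 × 2 × 52/12 = 130.0 to 20 × 2 × 52/12 = 173.3 per month, which is 1.9 to 2.5 times the truth.
- 5-10 meant per day but read per week: 5 × 52/12 = 21.7 to 10 × 52/12 = 43.3 per month, which is 0.31 to 0.63 times the truth.
- With 'per clinic day' printed, 5-10 gives 5 × 2 × 52/12 = 43.3 to 10 × 2 × 52/12 = 86.7 per month, which contains 69.3.

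**The case against.** The strongest reply is that these are copy-edits in a descriptive pilot, and a pilot is where such faults should surface. The protocol names no travel share, distance distribution or monthly caseload as an outcome, and it does not propose multiplying item 2 by item 3. That stands. The caseload ratios show how far apart two readings of one tick can lie; they are not errors in a planned estimate.

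A second reply is that the information is partly there. 'None' can be written on item 22's 'Other' line, and a number with its period on those of Annex II items 3 and 4. An unticked list is often read as 'not needed', and a form with items 21 and 24 answered but 22 and 23 blank points the same way. Annex I item 20 rates access, both forms have open questions, and the patient focus group can raise travel. The contrast between items 3 and 4 within one worker survives if that worker used one unit. All this reduces the loss. But nothing asks respondents to use the 'Other' lines this way, item 23 has none, and the content of the investigator's instructions in Section 5.1 is not stated.

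Third, the item 22 shift is smaller than sampling error: the nominal 95% half-width with 120 respondents is 1.96 × √(0.5 × 0.5/120), about 9 points at 50%, and about 8 points at 25% or 75%. That is correct and keeps the point low in severity. The shift is nevertheless one-directional when blanks are counted as 'no', and a larger survey using the same form would not remove it.

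**Conclusion.** The concern holds, at low severity. The missing 'No', the missing distances below 5 km and above 70 km, and the missing period are plain on the printed forms, and other items on those forms show how to avoid them.

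The travel share would shift by about 2 to 6 points if 10 to 20% of blanks are skips. The top distance band could read up to 30% instead of 10% if 20% of travellers go beyond 70 km and all tick the last box. One worker's monthly load could be misread by a factor of 0.31 to 2.5. All of these rest on assumed shares, and the first two vanish if nobody skips or travels outside the bands.

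A blank on item 22 can sometimes be interpreted from neighbouring answers. An unrecorded distance, or a caseload ticked without a period, cannot be reconstructed from the form. Sample size, eligibility and error rates are untouched.

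**What to change.** Reword four items before the forms are used, or before they are carried into the wider survey.

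- **Annex I item 22:** add a box such as 'No, I receive everything in this centre', and the instruction on multiple answers that item 21 already has.
- **Annex I item 23:** ask for the distance in kilometres, or use non-overlapping bands with open lower and upper ends. Direct it to those who did not answer 'No' to item 22, and say which centre is meant if several are used.
- **Annex II items 3 and 4:** print the same period in both, for example per clinic day so that item 2 converts it, and take a number or non-overlapping bands.

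If forms have already been completed, report blanks on items 22 and 23 separately instead of counting them as 'no', and do not convert the caseload bands to a monthly load.

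The cost is the rewording. No extra participants, staff or procedures are needed.

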**24. Are there facilities for psychological support in this hospital?**

A. Yes [ ]  
B. No [ ]

**25. How satisfied are you with the support received from the psychological support facilities?**

A. Very satisfied [ ]  
B. Satisfied [ ]  
C. Neither satisfied Nor dissatisfied [ ]  
D. Dissatisfied [ ]  
E. Very Dissatisfied [ ]

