## 3. Objectives

### 3.1. Primary objective

To assess the needs of SCD patients and health workers, with particular reference to the disease management in the clinical centre.

The study is intended as a pilot experience to verify the feasibility of the action through a structured survey. This is a descriptive, mixed method prospective questionnaire-based study. The study is intended as a pilot experience to verify the feasibility of the action through a structured survey.

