### 3.2. Sample size determination

As pilot experience, the questionnaires will be administered to 30 SCD patients or parents/legally designated representatives of children affected by SCD and 30 Professionals working with SCD patients (mainly doctors and nurses) in each centre for a total of 120 patients and 120 health workers. A focus group discussion will be run with the SCD patients/parents. Following the pilot study, a wider survey will be launched involve patients, parents and healthcare professionals in the whole country and in other centres involved in the project.

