### 3.3. Setting

The study will be conducted in the following four centres: Barau Dikko Teaching Hospital Kaduna State University (BDTH), Ahmadu Bello University Teaching Hospital Zaria (ABUTH), National Hospital Abuja (NHA), and Federal Medical Centre Katsina (FMC).

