### SECTION B

- 1. If you are a patient, what is your diagnosis? If you are a parent, what is the diagnosis of your child?**
  - A. Sickle cell disease [ ]
  - B. Sickle cell/b-thal [ ]
  - C. Sickle Beta-Plus Thalassemia [ ]
  - D. Other (please specify) \_\_\_\_\_
- 2. How is your/your child current transfusion regime?**
  - A. I am not transfused [ ]
  - B. I am regularly transfused [ ]
  - C. I am occasionally transfused [ ]
  - D. Other (please specify) \_\_\_\_\_
- 3. Where do you usually get information about Sickle Cell Disease?**
  - A. Websites
  - B. Social Networks
  - C. Scientific journals
  - D. TV
  - E. Radio
  - F. Leaflets/booklets
  - G. Doctor/nurse
  - H. Other patients
  - I. Relatives/friends
  - J. Religious leaders
  - K. Other (please specify) \_\_\_\_\_

---

**4. Please, indicate your main information source:** \_\_\_\_\_

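### Annex I item 25 has no 'If yes' routing and no 'not used' answer, and item 24 has no 'Don't know', so ratings of psychological support by users and non-users cannot be reliably separated

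*Protocol*

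**What the plan says.** Annex I, Section B, item 24 asks "Are there facilities for psychological support in this hospital" and offers two answers, yes and no. Item 25 follows directly: "How satisfied are you with the support received from the psychological support facilities". Its answers are five satisfaction grades, from very satisfied to very dissatisfied. It has no conditional lead-in, no skip instruction and no answer for someone who has not used the service.

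Conditional wording does appear elsewhere on the form: item 23 opens with a condition ("If yes, how far are the centres from your home").

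Section 5.1 has participants fill in the form themselves, in private, after instructions from the investigator, and drop it into a closed box. Section 3.1 gives the objective: "To assess the needs of SCD patients and health workers, with particular reference to the disease management in the clinical centre". Section 3.2 plans 30 patients or parents per centre, "in each centre for a total of 120 patients and 120 health workers", and section 3.3 names four centres.

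**The concern.** Item 25 presupposes that support was received. A respondent who answered no to item 24, or who knows of the service but never used it, has three ways to respond: leave the item blank, tick the neutral grade, or tick a dissatisfied grade because nothing was provided. The form does not record which of these happened.

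Item 24 has a related weakness. Whether a hospital has the facility is the same fact for everyone at that hospital, yet the item is put to individuals who may not know. Without a 'Don't know' box, a no can mean that the service is absent or that the respondent has not heard of it.

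What is at stake is how this part of a needs assessment can be read. A low satisfaction figure could reflect a poor service, an unused service or no service, and each calls for a different response. A larger survey is planned after the pilot; if the form is reused unchanged, the gap goes with it.

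**Working it through.** **Base.** 30 respondents per centre × 4 centres = 120, which reproduces the total in section 3.2.

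**What the two items can separate**

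| Respondent's situation | Item 24 | Item 25 | Identifiable afterwards? |
|---|---|---|---|
| Used the service | Yes | A grade | No, looks like the next row |
| Knows of it, never used it, ticks a grade | Yes | A grade | No |
| Knows of it, never used it, leaves a blank | Yes | Blank | No, looks like ordinary non-response |
| Reports no facility (absent, or unaware of it) | No | A grade or blank | Can be filtered out; the reason for the no is unknown |
| Does not know | Guess or blank | Any | No |

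A filter on item 24 = yes deals with the fourth row only.

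**Illustration of size.** The protocol gives none of the rates needed, so all of these are assumptions:
- *f* = share answering yes to item 24
- *u* = share of those who have used the service
- *s* = 70%, the share of users who are satisfied

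Suppose first that everyone answers item 25 and every non-user ticks the neutral grade. Then:
- unfiltered satisfied share = *s* × *f* × *u*
- share filtered on item 24 = yes is *s* × *u*

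| *f* | *u* | Expected users (120 × *f* × *u*) | Unfiltered | Filtered | Users only |
|---|---|---|---|---|---|
| 25% | 25% | 7.5 | 4.4% | 17.5% | 70% |
| 50% | 50% | 30 | 17.5% | 35.0% | 70% |
| 75% | 75% | 67.5 | 39.4% | 52.5% | 70% |
| 100% | 100% | 120 | 70% | 70% | 70% |

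With *f* and *u* each between 25% and 100%, the unfiltered figure runs from 4.4% to 70% and the filtered figure from 17.5% to 70%. True satisfaction among users is 70% throughout.

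**Dependence on what non-users do.** Take *f* = *u* = 50%: 60 answer yes, of whom 30 are users and 30 non-users, and 0.70 × 30 = 21 users are satisfied. Among the 60:
- all 30 non-users tick neutral: 21/60 = 35.0%
- 15 tick neutral and 15 leave a blank: 21/45 = 46.7%
- all 30 leave a blank: 21/30 = 70.0%
- all 30 tick a satisfied grade: (21 + 30)/60 = 85.0%

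So the distortion may be absent, downward or upward, and the collected data cannot show which.

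**Precision after the change.** With 30 identified users and 70% satisfied, the 95% half-width is 1.96 × √(0.70 × 0.30 / 30) = 16.4 percentage points. The denominator is small, but the figure has a clear meaning.

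**The case against.** The strongest reply is that much of this can be handled with what is already collected. Items 24 and 25 are on the same coded form, so they can be cross-tabulated and item 25 reported only where item 24 is yes. A statistical analysis plan, which is not at hand, could set that denominator. This stands for respondents who report no facility. It does not help with those who know of the service and never used it, because use is not recorded.

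Second, item 25 speaks of support received, and the investigator gives completion instructions, so some non-users may leave it blank. That also stands: mixing is likely, not certain. But section 5.1 describes no routing instruction for this item.

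Third, unmet need has other outlets. The open question closing Annex I and focus group questions 4 and 6 (Annex III) allow it to be raised. Items 6 and 7 ask about support after and at diagnosis, and some answers may touch on psychological help. None of these names psychological support, and none yields a proportion of respondents who used or needed it.

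Fourth, a contrast with item 2, where "I am not transfused" is an answer, is weak: that is a category of a transfusion question, not an opt-out from a satisfaction scale. Item 23 is the better comparison.

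Finally, this is a descriptive pilot, the point concerns two of 27 numbered items, and no decision rule rests on item 25. That limits the weight of the point but does not remove it.

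**Conclusion.** The point holds in a limited form. As written, item 25 gives a satisfaction figure in which users and non-users cannot be reliably separated, blanks are ambiguous, and item 24 = no mixes absence with lack of awareness. No closed item in Annex I measures use of, or need for, psychological support. Later analysis cannot repair this, because the information on use is not collected.

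The size is unknown. The figures above rest on assumed shares and an assumed 70% satisfaction among users; they show what could happen, not what will.

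A reader might infer more than the protocol supports:
- That the form has no way to report a missing facility. It has one: the no answer to item 24.
- That unmet need cannot be captured at all. It can, qualitatively, through the open question and the focus group.
- That ratings will certainly be mixed, or that a particular drop in satisfaction can be predicted. Either conclusion requires assumptions about usage and about what non-users tick, and a calculation on all 120 also ignores the available filter.
- That the primary objective fails. The objective covers needs in general, and psychological support is one part of it.

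**What to change.** In Annex I:
- Item 24: add 'Don't know'.
- Item 25: begin with 'If yes' and add the answer 'I/my child have not used it'.
- Reporting: give item 25 satisfaction among users only, and show the number of non-users beside it.
- Optional: add one tick item on whether psychological support was needed but not received. This adds content the present form does not collect, so it is the authors' choice. Without it, the form gives no proportion with unmet need.

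The cost is two answer boxes and a routing phrase, plus one tick item if the option is taken. The downside is a smaller but valid denominator for item 25, and hence a wider interval.

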**26. How can you recommend this hospital to relatives and friends?**

A. Definitely no [ ]  
B. Probably no [ ]  
C. Definitely yes [ ]  
D. Probably yes [ ]

**27. How would you describe your/your child current health?**

E. Very poor [ ]  
F. Neither poor nor good [ ]  
G. Good [ ]  
H. Excellent [ ]

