## 5. Study procedure

### 5.1. Questionnaire completion

After obtaining the informed consent, subjects (patients, parents/legally designated representatives and healthcare professionals) will be asked to complete the questionnaire. Two questionnaires have been developed, one addressed to patients, parents, legally designated representatives (Annex I) and another one for healthcare professionals (Annex II)

The following measures will be adopted to reduce the interviewer effect:

- The investigator will give instructions to complete, but questionnaires will be self-completed.
- Participants will have time to complete the questionnaire in a private setting.
- Completed questionnaires will be blindly deposited in a closed box. This will be thus safeguarded by the investigators.
- Completed questionnaires will be returned to the coordinating investigator for analysis.

Questionnaires will be pseudonymised: an alphanumeric code will be indicated on each questionnaire and reported on the corresponding informed consent form.

All the study investigators are researchers/officers in the centres not involved in patients' clinical management. The veracity and consistency of responses are of paramount importance for the

---

validity of the study and the improvement of the management of SCD patients: all the actions necessary to allow the participants to freely express themselves will be adopted.

Together with the questionnaire, participants will receive information about the time and venue for the focus group discussion (Annex III). For those who are willing, reminders about the focus group will be sent by e-mail/phone.

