**14. How satisfied are you with the level of responsibility you have?**

- A. Very satisfied [ ]
- B. Satisfied [ ]
- C. Neither satisfied nor dissatisfied [ ]
- D. Dissatisfied [ ]
- E. Very Dissatisfied [ ]

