**15. How satisfied are you with on the decision-making autonomy you have?**

---

---

A. Very satisfied [ ]  
B. Satisfied [ ]  
C. Very Dissatisfied [ ]  
D. Dissatisfied [ ]  
E. Neither satisfied nor dissatisfied [ ]

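### Annex I item 27 (current health) offers no *Poor* option, so that level of health cannot be recorded; two other items have complete scales printed out of order

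*Protocol*

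**What the plan says.** Annex I, Section B, item 27 asks "How would you describe your/your child current health" and offers four answers, lettered E to H: *Very poor*, "F. Neither poor nor good", *Good*, *Excellent*.

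Two other items have complete scales in an unusual order:

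- **Annex II item 15** (decision-making autonomy) starts with the two satisfied levels, continues with "C. Very Dissatisfied" and *Dissatisfied*, and ends with "E. Neither satisfied nor dissatisfied". In item 14, just before it, the neutral option is third and the last is "E. Very Dissatisfied".
- **Annex I item 26** (recommending the hospital) gives *Definitely no*, *Probably no*, "C. Definitely yes" and only then *Probably yes*.

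On administration, section 5.1 says: "The investigator will give instructions to complete, but questionnaires will be self-completed". On what comes next, section 3.2 says: "Following the pilot study, a wider survey will be launched".

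**The concern.** Item 27 has one unfavourable level against two favourable ones. Its neutral label names poor as one pole of the scale, yet *Poor* cannot be ticked. The information is lost when the respondent answers, so no later coding or analysis restores it. The direction of the distortion is not certain: those who move to *Very poor* overstate severity, and those who move to neutral shrink the unfavourable share.

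Items 15 and 26 are a different and lesser matter. All their levels are present, so tabulation by label is correct. The risks are that a health worker who has just answered items 13 and 14 in the usual order ticks item 15 by position, and that someone later scores either item by letter.

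**Working it through.** The protocol states no figure for these items, so there is none to reproduce. The check compares the printed scales and then sizes the effect under stated assumptions.

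**1. Is *Poor* really absent?** The letters of item 27 run E, F, G, H without a gap and continue from A–D of item 26. A line lost in converting the document would normally break the lettering, so the option appears never to have been printed.

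| Poor/good item | Unfavourable | Neutral | Favourable |
|---|---|---|---|
| Annex I item 19 | 2 | 1 | 2 |
| Annex II items 8, 11, 12, 16 (each) | 2 | 1 | 2 |
| Annex I item 27 | 1 | 1 | 2 |

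**2. How unusual is the order of Annex II item 15?** The other satisfaction items with five levels are Annex I items 5, 7–10, 12–17 and 25 (12 items) and Annex II items 5, 10, 13 and 14 (4 items). All 16 run from very satisfied through neutral to very dissatisfied.

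**3. Size for item 27.** There are 120 patients/parents, 30 in each of four centres (section 3.2). Let *p* be the share who would have chosen *Poor*, and *f* the fraction of them who move to neutral while the rest move to *Very poor*. The documents do not give *p*; 10–30% is assumed for illustration.

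- Answers affected: 0.10 × 120 = 12 to 0.30 × 120 = 36. Per centre: 0.10 × 30 = 3 to 0.30 × 30 = 9.
- Fall in the unfavourable share = *p* × *f*:
  - *f* = 0: 0 points
  - *f* = 0.5: 5 to 15 points
  - *f* = 1: 10 to 30 points
- A blank answer, counted against all 120, has the same effect on this share as a move to neutral.

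**4. Size for items 15 and 26, only if scored by letter (A = 1, B = 2, and so on).**

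*Item 15.* Letter scoring gives very dissatisfied 3 and neutral 5; the proper order gives neutral 3 and very dissatisfied 5. The mean shifts by 2 × (neutral share − very-dissatisfied share). Illustrative splits, in the order very satisfied / satisfied / neutral / dissatisfied / very dissatisfied:

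- 20/40/20/15/5%: 2.75 − 2.45 = 0.30
- 20/40/10/20/10%: 2.60 − 2.60 = 0
- 20/40/25/10/5%: 2.80 − 2.40 = 0.40

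The shift is therefore 0 to 0.4 for an assumed gap of 0–20 points. It turns negative if the very dissatisfied outnumber the neutral.

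*Item 26.* Letter scoring gives definitely yes 3 and probably yes 4; the proper order reverses these. The mean shifts by (probably-yes share − definitely-yes share). Illustrative splits, in the order definitely no / probably no / probably yes / definitely yes:

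- 10/20/50/20%: 3.10 − 2.80 = +0.30
- 10/20/20/50%: 2.80 − 3.10 = −0.30

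Coded by label, both shifts are 0.

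**The case against.** The strongest reply is that little depends on item 27. The primary objective concerns needs in disease management at the centre, the study is a descriptive pilot, and no endpoint, score or subgroup is tied to this item. Ratings of care, communication, laboratory, treatment and access come from other items. A respondent in poor health can still give an unfavourable answer by ticking *Very poor*. All of this is fair and limits the weight of the point. It does not restore the missing level, and item 27 is the only overall rating of current health on the form.

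For items 15 and 26, the letter-scoring figures describe an error that nothing in the protocol says will happen. A coding key commonly sits in an analysis or data-management document, so its absence from the protocol is no fault. Health workers also see only the four other satisfaction items in Annex II, not all 16, and a page break may separate the stem of item 15 from its options. That stands: what remains for these two items is print order and a mis-ticking risk in item 15 that cannot be sized.

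Finally, the protocol does not say that the wider survey will reuse these forms, and finding such faults is part of what a pilot is for. That is a reason to correct the forms now, not to leave them.

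**Conclusion.** The point holds and is minor. Item 27 lacks a level that the protocol's other poor/good items all have, and on a self-completed form its distribution will be distorted at the lower end in a way that analysis cannot repair. The 12–36 affected answers and the 0 to 30 point fall rest wholly on the assumed 10–30% share and on where those respondents move; they show a possible scale and are not estimates. Items 15 and 26 are confirmed as complete but out of order. They cause no loss if coded by label, apart from possible mis-ticks in item 15.

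**What to change.** **Before printing:**

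- Item 27, Annex I: add *Poor* between *Very poor* and the neutral option, and letter the five options A–E. *Excellent* can stay.
- Item 15, Annex II: use the order of item 14.
- Item 26, Annex I: order as *Definitely no*, *Probably no*, *Probably yes*, *Definitely yes*.

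**If forms are already in use:** code items 15 and 26 by label, report item 27 with its limitation, and correct the form before the wider survey.

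**Cost:** before printing, one added option, new letters for item 27 and two reordered lists. Once forms are in use, item 27 answers from the old and new versions cannot be pooled without a note. Items 26 and 27 would still run from unfavourable to favourable, opposite to the satisfaction items; reversing them is optional.
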